# 6.12.2. Extent of Exposure

Exposure to therapy will be represented as the total number of complete and incomplete infusions and will be summarized using descriptive statistics.

### 6.12.3. Adverse Events

Summaries of AEs will include the number of participants with at least 1 AE for each treatment group. When reporting by System Organ Class (SOC) and PT, the reports will present the SOC in alphabetical order, while PTs within the SOC will be presented in order of overall decreasing frequency of occurrence overall. A patient with multiple AEs (different PTs) coded to the same SOC will be counted only once for that SOC, but will be counted each time for different PTs within that SOC. A patient with separate events of the same PT will be counted only once in the frequency tables for that PT.

Adverse events will be coded according to the Medical Dictionary for Regulatory Activities (MedDRA) and summarized by SOC, PT, severity, and relationship to IP as assessed by the investigator. For each event classification term, the number of subjects experiencing a treatment-emergent AE (TEAE) with that classification term will be tabulated.

In an overview table, the number and percentage of participants who experienced a TEAE, serious adverse event (SAE), AE related to study drug, died due to an AE, discontinued from the study treatment, or discontinued from the study due to an AE will be summarized. Treatment-emergent AEs may be reported separately for the treatment period and follow-up periods.

### Treatment-Emergent Adverse Events

A TEAE is defined as an event that first occurred or worsened in severity after baseline. The MedDRA Lowest Level Term (LLT) will be used in the treatment-emergent computation. The

maximum severity for each LLT during the baseline period will be used as baseline. While unusual, it is possible to have a missing severity for events. For events with a missing severity during the baseline period, it will be treated as "mild" in severity for determining treatment emergence. Events with a missing severity during the postbaseline period will be treated as "severe" and treatment emergence will be determined by comparing with baseline severity. Missing severity will be reported as missing, without imputation, for data listing.

Additional types of AEs to be summarized are described in Table PYAB.6.8.

Table PYAB.6.8. Additional Types of Adverse Events to be Summarized

Event Type	Summary Method
SAEs	SAEs will be summarized by SOC and PT. These reports will also include
	the total number of SAE for each SOC and PT.
TEAEs Resulting in Death	If there are any TEAEs that result in death, a listing of all deaths will be
	provided. In addition, a summary table may also be created by PT in order of
	decreasing frequency of preferred term.
TEAEs Leading to Study Drug	TEAEs for which the action taken with medication is 'Drug Withdrawal'
Discontinuation	will be identified as TEAEs that lead to study drug discontinuation. The
	TEAEs that lead to study drug discontinuation will be summarized by SOC
	and PT for the safety population. A by-patient listing of the TEAEs that lead
	to study drug discontinuation will also be provided.
Treatment-Related TEAEs	Every AE will be assessed by the investigator for its relationship to the
	randomly assigned study treatment.
TEAEs by Maximal Severity	Every AE will be graded by the investigator as mild, moderate, or severe, so
	for each patient the greatest severity observed can be obtained by comparing
	the severity of all of a patient's TEAEs that share the same SOC or PT. A
	table of TEAEs by maximal severity will be prepared by SOC and PT.
TEAEs (Not Including Serious)	The most common nonserious TEAEs will be summarized. All PT that occur
	in at least 5% of the safety population participants, when not counting the
	serious TEAEs, will be tabulated by SOC and PT. These reports will also
	present the total number of TEAEs for each SOC and PT.

Additional Types of Adverse Events to be Summarized

Event Type	Summary Method
Infusion Reactions	Treatment-emergent infusion reactions will be summarized by PT within
	high level term (HLT).

Abbreviations: AE = adverse event; PT = preferred term; SAE = serious adverse event; SOC = System Organ Class; TEAE = treatment-emergent adverse event.

### SOC Mapping

Medical Dictionary for Regulatory Activities PTs are assigned to a SOC through primary mappings (defined by MedDRA). Thus, MedDRA PTs will appear in only 1 SOC.

#### Events Not Summarized

Events considered related by the investigator will not be summarized for CSR. Medical representatives may use the relatedness assessment when reviewing individual cases.

# 6.12.4. Deaths, Other Serious Adverse Events, and Other Notable Adverse Events

The following are "notable" events, from start of study drug through end of study participation:

deaths

serious adverse events, and

discontinuations of study treatment due to AEs.

Narratives (patient-level data and summary paragraph) will be provided for participants in the safety population with at least 1 notable event.

Safety topics of interest are not considered notable events, unless 1 of the above criteria is met. Displays with individual patient-level data will be created for safety topics of interest using various formats such as a customized listing and/or a customized graphical patient profile as specified in the section associated with the safety topic of interest. Medical case summaries/vignettes will be provided if deemed relevant for the discussion of the safety topic of interest.

# 6.12.5. Hospitalization, Clinical Events, Clinical Status, and Environmental Risk Factors

The following events (observed at any time point during the study treatment period) will be summarized as described in Sections 6.16.2.1, 6.16.2.2, 6.16.2.3, and Section 6.16.2.4.

proportion of participants hospitalized

duration of hospitalization (DOH; in days)

proportion (percentage) of participants admitted to Intensive Care Unit (ICU), and proportion (percentage) of participants requiring mechanical ventilation (oxygen source = "Intubation/Mechanical Ventilation")

All hospitalization events, procedures of special interest, and environmental risk factors will be listed.

In the event that a participant has an ongoing hospitalization event at the time of study disposition, the hospitalization end date will be imputed to the study disposition date.

# 6.12.6. Clinical Laboratory Evaluation

Laboratory analyses will include planned analytes only. Planned analytes are those specified in the protocol (See Protocol Appendix 2). However, unscheduled measurements of planned analytes will be included/excluded as specified in the relevant sections. Examples of unplanned measurements include those that the clinical investigator orders as a repeat test or "retest" of a laboratory test in case of an abnormal value, and those the investigator orders for a "follow-up visit" due to clinical concerns. Some planned analytes are intended for individual case reviews and will not be included in group-level summaries.

# 6.12.7. Vital Signs and Other Physical Findings

The planned summaries are provided in Table PYAB.6.9. The measurements analyzed for vital signs and physical characteristics include systolic blood pressure (BP), diastolic BP, pulse, weight, peripheral oxygen saturation (SpO2), respiratory rate, fraction of inspired oxygen (FiO2), and temperature if data warrant.

The criteria for identifying subjects with treatment-emergent abnormalities are based on Table PYAB.6.10.

Some of the analyses of vital signs may be incorporated into interactive display tools instead of or in addition to a static display. Any display described in Table PYAB.6.9 and not provided would be available upon request. For example, box plots for observed values, scatter plots, and shift tables could be provided as interactive displays for medical review.

Table PYAB.6.9. Tables and Figures Produced to Support Vital Signs and Physical Characteristics

Analysis Type	Analysis Details		
Box plots for observed	Includes participants who have both a baseline and a postbaseline measurement from a		
values by visit	planned visit.		
	Unplanned measurements will be excluded.		
	Last baseline will be used.		
	Descriptive summary statistics will be included in a table below the box plot.		
	No inferential statistics.		
Box plots for change	Includes participants who have both a baseline and a postbaseline planned		
from baseline values	measurement.		
by visit	Unplanned measurements will be excluded.		
	Last baseline will be used.		
	Descriptive summary statistics will be included in a table below the box plot.		
	Change from last baseline to last postbaseline will also be summarized within the box		
	plot of changes (rightmost column), and descriptive summary statistics will be included		
	in a table below the box plot along with a p-value using the ANCOVA model.		
Scatter plots of	Each study individually and studies combined will be displayed.		
baseline-by-maximum	Includes participants who have both a baseline and postbaseline observation.		
values and baseline-by-	Unplanned measurements will be included.		
minimum values	Lines indicating the reference limits will be included.		
	Max versus Max: Maximum baseline versus maximum postbaseline.		
	Min versus Min: Minimum baseline versus minimum postbaseline.		
Summary tables for	Limits provided by the central lab service will be used to define low and high.		
shifts to high/low	Normal/high to low: Includes the number and percentage of participants by treatment		
	whose minimum baseline result is normal or high and whose minimum postbaseline		
	result is low.		
	Denominator equals participants whose minimum baseline result is normal or high and		
	who have at least 1 postbaseline result.		
	Normal/low to high: Includes the number and percentage of participants by treatment		
	whose maximum baseline result is normal or low and whose maximum postbaseline		
	result is high.		
	Denominator equals participants whose maximum baseline result is normal or low and		
	who have at least 1 result during the treatment period.		
	
 
Statistical comparisons will be included.
 
		

Abbreviations: ANCOVA = analysis of covariance; Max = maximum; Min = minimum.

Systolic BP, mm Hg Diastolic BP, mm Hg Pulse/HR bpm Age (supine or sitting (supine or sitting) (supine or sitting forearm at heart level) forearm at heart level) Infant <2 Low ≤70 and decrease ≥15 <35 and decrease ≥10 <70 and decrease ≥25 Higha ≥108 and increase ≥15 ≥74 and increase ≥10 >190 and increase ≥25 Child 2-4 Low ≤75 and decrease ≥15 ≤40 and decrease ≥10 <60 and decrease ≥25 Higha ≥110 and increase ≥15 ≥76 and increase ≥10 >160 and increase ≥25 Child 5-9 ≤80 and decrease ≥15 ≤45 and decrease ≥10 <60 and decrease ≥25 Low Higha ≥119 and increase ≥15 ≥78 and increase ≥10 >150 and increase ≥25 Child 10-12 ≤85 and decrease ≥20 Low ≤50 and decrease ≥10 <60 and decrease ≥25 Higha ≥126 and increase ≥20 ≥82 and increase ≥10 >140 and increase ≥25 Adolescent Low ≤90 and decrease ≥20 ≤50 and decrease ≥10 <50 and decrease ≥15 ≥129 and increase ≥20 >13 Higha ≥86 and increase ≥10 >120 and increase ≥15

Table PYAB.6.10. Categorical Criteria for Abnormal Treatment-Emergent Blood Pressure and Pulse Measurement in Pediatric Individuals

Abbreviations: BP = blood pressure; bpm = beats per minute. HR = heart rate

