# 6.1.1. Analysis Populations

Patient populations are defined in Table PYAB.6.1 along with the analysis to be used to conduct. The treatment groups and inferential comparisons described in Table PYAB.6.1 will be used unless otherwise specified.

Table PYAB.6.1. Analysis Populations

Population	Description	
Entered	Definition: All participants who signed informed consent/assent.	
	Purpose: Used for disposition analysis.	
	Treatment Groups: None	
	Inferential Comparisons: None	
Per-Protocol	Definition: All participants in the efficacy population who do not meet any of the following criteria:	
	did not meet an inclusion criterion; or	
	met an exclusion criterion.	
	Purpose: Used for sensitivity analyses for the primary and key secondary endpoints.	
	Treatment Groups (Short Label):	
	Bebtelovimab weight-based dosing.	
	Inferential Comparisons:	
	None, as this is a single-arm cohort.	
Efficacy	Definition: All enrolled participants who received study intervention and provided at least 1 postbaseline efficacy measurement.	
	Purpose: Used for efficacy variable analyses.	
	Treatment Groups (Short Label):	
	Bebtelovimab weight-based dosing.	
	Inferential Comparisons:	
	None, as this is a single-arm cohort	
Safety	Definition: All enrolled participants who received any amount of study intervention.	
	Purpose: Used for safety analyses, analyses of COVID-19-related deterioration and hospitalization events.	
	Treatment Groups (Short Label):	
	Bebtelovimab weight-based dosing.	
	Inferential Comparisons:	
	None, as this is a single-arm cohort.	
Pharmacokinetic and PK/PD	Definition: All enrolled participants who received study intervention and have	
(exposure-response	at least 1 post dose PK sample.	
relationships)	Purpose: Used for PK analyses.	
	Treatment Groups (Short Label):	
	Bebtelovimab weight-based dosing.	
	Inferential Comparisons:	
	None, as this is a single-arm cohort.	

Abbreviations: COVID-19 = coronavirus disease 2019; PD = pharmacodynamic; PK = pharmacokinetic; SC = subcutaneous.

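### SAP Table PYAB.6.9 orders p-values and statistical comparisons for vital signs and weight in one uncontrolled arm, and takes shift limits from the central laboratory

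*SAP*

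**What the plan says.** SAP 6.12.7 first lists what is covered: "The measurements analyzed for vital signs and physical characteristics include systolic blood pressure (BP), diastolic BP, pulse, weight, peripheral oxygen saturation", then respiratory rate, FiO2, "and temperature if data warrant". Weight carries no such condition.

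Table PYAB.6.9 then sets the displays:
- **Box plots of change.** Change from last baseline to last postbaseline is summarised "in a table below the box plot along with a p-value using the ANCOVA model".
- **Shifts to high or low.** "Limits provided by the central lab service will be used to define low and high", percentages are given by treatment, and "Statistical comparisons will be included".
- **Box plots of observed values.** The same table rules out inferential statistics here.

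Just above the table, 6.12.7 says: "The criteria for identifying subjects with treatment-emergent abnormalities are based on Table PYAB.6.10". That table gives age-banded limits for systolic BP, diastolic BP and pulse only.

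Elsewhere in the SAP:
- Table PYAB.6.1 (6.1.1) gives the inferential comparisons for the safety population as "None, as this is a single-arm cohort". The text above that table lets it yield where the SAP specifies something else.
- Section 6.1.4 describes an ANCOVA with the baseline value as its only term.
- Section 6.5 says multiplicity control does not apply.

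Protocol addendum Section 9.4.1 makes descriptive summaries the default, overall and by age group, with a similar exception clause.

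**The concern.** A p-value needs a stated null hypothesis, and a comparison needs something to compare. Neither exists here: there is one arm, no treatment term in the model, no named test for the shifts and no stated alpha. Whoever programs the table must choose the hypothesis, possibly after the data exist.

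Whichever is chosen, it will not isolate the drug. Children enter with acute symptomatic COVID-19. Vital signs and weight are scheduled to Day 60, so the last postbaseline value will usually fall in convalescence. The rationale for protocol revision 4.2 itself says that newborn and infant weight changes markedly over the first weeks and months. A small p-value in a safety table could be read as a treatment-related change when it reflects recovery or growth.

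The limits are a separate defect. The Schedule of Activities assigns the central laboratory to haematology, chemistry, swab, PK and ADA samples, and not to vital signs. The documents therefore name no source for the limits the shift row relies on.

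**Working it through.** The plan gives no figure for these analyses, so there is none to reproduce. Its planned size of about 50 children under 12 years, with at least 5 per age group (SAP 5.3), is used as an input. All effect sizes and SDs below are assumptions, because the documents state none.

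**1. What the ANCOVA can test.** With only baseline in the model, change = a + b × baseline + error. Testing a (with baseline centred) asks whether the mean change is zero, so recovery and growth count against the null. Testing b asks whether change depends on baseline, which regression to the mean produces by itself. No coefficient represents the drug.

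**2. How small a change is enough.** I approximate the first test by a one-sample t, two-sided 0.05: t = m/(s/√n). Adjusting for baseline cannot increase the residual sum of squares, so apart from one degree of freedom this does not overstate sensitivity.
- n=50: |m|/s must exceed 2.010/√50 = 0.284. A true ratio of 0.40 gives 80% probability of p<0.05.
- n=5: |m|/s must exceed 2.776/√5 = 1.24. A true ratio of 1.68 gives 80%.

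**3. Weight to Day 60, no drug effect, n=50.** Mean gains are assumed for 0 to <2, 2 to <6 and 6 to <12 years. Overall mean m = Σ(weight × gain), SD = √(residual² + between-group variance), and the probability comes from the noncentral t.

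| Age mix (n) | Gains, kg | Residual SD, kg | m, kg | m/SD | P(p<0.05) |
|---|---|---|---|---|---|
| 5, 5, 40 | 0.4, 0.2, 0.2 | 0.8 | 0.22 | 0.27 | 0.48 |
| 5, 5, 40 | 0.4, 0.2, 0.2 | 0.4 | 0.22 | 0.54 | 0.96 |
| 17, 17, 16 | 0.4, 0.2, 0.2 | 0.8 | 0.27 | 0.33 | 0.64 |
| 40, 5, 5 | 0.4, 0.2, 0.2 | 0.8 | 0.36 | 0.45 | 0.87 |
| 5, 5, 40 | 0.8, 0.3, 0.4 | 0.8 | 0.43 | 0.53 | 0.96 |

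First row: m = (5×0.4 + 45×0.2)/50 = 0.22; between-group variance = 0.1×0.18² + 0.9×0.02² = 0.0036; SD = √(0.64 + 0.0036) = 0.80. Across the three mixes, every scenario with the middle gains or higher ones (1.2, 0.4, 0.5) gives at least 0.95.

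**4. Temperature, no drug effect, n=50.** A fraction f is febrile at baseline and falls by d; the rest do not change. m = f·d and SD = √(s² + f(1−f)d²). The range runs from d=0.8 °C with s=0.7 to d=1.5 °C with s=0.5.

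| f | m/SD | P(p<0.05) |
|---|---|---|
| 10% | 0.11 to 0.22 | 0.12 to 0.34 |
| 20% | 0.21 to 0.38 | 0.30 to 0.76 |
| 30% | 0.30 to 0.53 | 0.56 to 0.96 |
| 50% | 0.50 to 0.83 | 0.93 to 1.00 |

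**5. Pulse.** The result turns on the assumed values. At n=50, −5 bpm with SD 15 gives t = −2.36, p=0.022; −5 with SD 20 gives p=0.083; −3 with SD 15 gives p=0.16. At n=5, −5 with SD 15 gives p=0.50.

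**6. Number of tests.** Eight measurements are listed. If nothing changed and the tests were independent, at least one p<0.05 would occur with probability 1 − 0.95⁸ = 0.34.

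**7. The limits.** A shift table must label each baseline value low, normal or high. Table PYAB.6.10 cannot do that, because its criteria combine a level with a change (for infants, low systolic BP is ≤70 with a fall of ≥15). It can identify a treatment-emergent abnormality, but only for BP and pulse. So the shift row has no identified limits, and Table PYAB.6.10 cannot simply be substituted.

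**The case against.** A reader might infer that recovery and growth will be reported as significant drug effects. The documents do not support that. The SAP sets no alpha for these p-values and nowhere says how they will be interpreted. Temperature is conditional, and SAP 6.1 says not every display will be in the CSR. The probabilities in steps 3 and 4 include values well below 1, and small age groups have little sensitivity. This stands: the right word is can.

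A second objection is that Table PYAB.6.1 and the protocol's descriptive default both allow exceptions, so Table PYAB.6.9 is a specified exception and not a contradiction. Formally that is right. It does not rescue the instruction, because an exception still needs a contrast or a stated null, and this one has neither.

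A third is that the wording is probably template carry-over and therefore inoperative. References to studies combined and to results by treatment point that way. That explains the text but leaves it in force for whoever builds the tables.

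Fourth, two definitions of abnormality are not in themselves a conflict, since a shift and a treatment-emergent abnormality are different displays. That stands. What remains is that the shift limits have no identified source. They affect the shift categories only and have no bearing on the ANCOVA p-value.

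Finally, the safety analyses in protocol addendum Section 9.4.3 concern adverse events, interrupted dosing and hypersensitivity, and no decision rule uses these p-values. That stands and limits the severity.

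**Conclusion.** The point holds in limited form. Table PYAB.6.9 orders inference that a single arm with a baseline-only model cannot support. The shift comparisons have no contrast, and the p-value has no stated null and cannot separate drug effect from recovery, growth or regression to the mean.

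On the assumed inputs, p<0.05 with no drug effect is likely but not certain for weight (0.48 to 1.00). For temperature it depends on how many children are febrile at baseline (0.12 to 1.00) and arises only if temperature is analysed. These ranges rest on assumed growth, fever prevalence and SDs, a two-sided 0.05 level, n=50, and reading the p-value as a test of mean change. The missing contrast rests on none of these.

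The central-laboratory limits are a separate, smaller defect. The primary PK endpoint and the adverse-event summaries are untouched. Severity is low.

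**What to change.** In SAP Table PYAB.6.9:
- Delete the ANCOVA p-value from the change-from-baseline row and the statistical comparisons from the shift row.
- Report change as n, mean, SD, median and range, overall and by age group, with a statement that changes cannot be attributed to the drug. Do not simply swap the p-value for a 95% CI: a t-based interval excludes zero exactly when that t-test gives p<0.05. Section 6.1.4 includes safety variables in its ANCOVA and reports an interval, so Table PYAB.6.9 should say that it is the exception, or label any interval as descriptive.
- Delete the central-laboratory-limit shift row for vital signs. For BP and pulse, report the number and percentage meeting the treatment-emergent criteria of Table PYAB.6.10. For the other measures give descriptive summaries only, unless age-appropriate limits are named.

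The cost is SAP wording and somewhat less programming. Sample size, data collection and the primary analysis do not change.

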2.7.1. Section 5.1. Inclusion Criteria

Participants are eligible to be included in this addendum only if all of the following criteria apply:

1. This criterion is not applicable to participants in this addendum
2. This criterion is not applicable to participants in this addendum
3. This criterion is not applicable to participants in this addendum
4. Must have first positive result sample of current SARS-CoV-2 viral infection ≤ 3 days prior to start of the administration
5. Are males or females
Reproductive and Contraceptive requirements are provided in the main PYAB protocol, Section 10.4, Appendix 4. Contraceptive use by males or females should be consistent with local regulations for those participating in clinical studies.
6. The participant and/or legally authorized representative understand and agree to comply with planned study procedures
7. The participant and/or legally authorized representative agree to the collection of nasopharyngeal swabs and venous blood
8. The participant or legally authorized representative give signed informed consent and/or assent as described in the main PYAB protocol, Section 10.1.3 which includes compliance with the requirements and restrictions listed in the informed consent form (ICF) and in this protocol.
27. This criterion is not applicable for participants in this addendum
28. This criterion is not applicable for participants in this addendum
36. Are 0 (≥ 38 weeks gestational age and ≥ 3.3 kg) to <12 years of age at the time of screening, or are 12 to 17 and weighing <40 kg.
37. Have mild to moderate COVID-19 disease, including one or more of the following symptoms, within the last 7 days (FDA February 2021; CDC January 2022; CDC March 2022.)
 - shortness of breath or difficulty breathing
 - fever
 - sore throat
 - nausea
 - diarrhea
 - nasal congestion or runny nose
 - chills
 - malaise
 - vomiting
 - cough

- tiredness
- headache
- new loss of taste
- muscle or body aches and pain
- new loss of smell, or
- poor appetite or poor feeding (especially in babies under 1 year old).

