# 5.3. Determination of Sample Size

### Sample Size

There is an urgent unmet need among pediatric patients since there are no approved vaccines for the prevention of COVID-19 in pediatric patients <6 months of age and no FDA-approved therapies effective for treatment of the Omicron variant in patients <12 years or outside the existing bebtelovimab EUA criteria. Consequently, this study will include SARS-CoV-2 positive pediatric patients with mild to moderate disease that are 0 (≥38 weeks gestational age and ≥ 3.3 kg) to <12 years of age, or 12 to 17 years of age and weighing <40 kg.

The planned sample size is approximately 50 participants that are 0 ( $\geq$ 38 weeks gestational age and  $\geq$ 3.3 kg) to 12 years of age, with a minimum of 5 participants in each of these age groups

0 to <2

2 to <6 years, and

6 to <12 years

Participants who are 12 to 17 years of age and weighing less than 40 kg can be enrolled into the study until approximately 50 participants that are 0 ( $\geq$ 38 weeks gestational age and  $\geq$  3.3 kg) to 12 years of age are fully enrolled.

Fifty participants would provide adequate study power to target a 95% confidence interval within 60% to 140% of the geometric mean estimates of clearance and volume of distribution (Wang et al. 2012) for bebtelovimab as can be seen in Figure PYAB.5.2.

Participants who are 12 to 17 years (and weighing <40 kg) can be enrolled, up to approximately 20 participants. Enrollment for this group may continue (up to 20 participants) until approximately 50 participants <12 years have been fully enrolled.

[figure not shown]

Figure PYAB.5.2. Estimated study power to target a 95% confidence interval within 60% to 140% of the geometric mean estimates of clearance and volume of distribution.

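### As read, SAP Table PYAB.6.10 has no row for age 13, so an eligible 13-year-old has no categorical blood pressure or pulse criterion (minor)

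*SAP*

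**What the plan says.** SAP section 6.12.7 gives the table an operative role: "The criteria for identifying subjects with treatment-emergent abnormalities are based on Table PYAB.6.10". Its caption limits the scope to blood pressure and pulse: "Categorical Criteria for Abnormal Treatment-Emergent Blood Pressure and Pulse Measurement in Pediatric Individuals".

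The rows run Infant <2, Child 2-4, Child 5-9, Child 10-12 and Adolescent. Each gives a low and a high criterion for systolic pressure, diastolic pressure and pulse, which makes six criteria per row. The two oldest rows matter here:

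- The low criteria of the second-oldest row read "Child 10-12 ≤85 and decrease ≥20 Low ≤50 and decrease ≥10 <60 and decrease ≥25".
- The low criteria of the oldest row read "Adolescent Low ≤90 and decrease ≥20 ≤50 and decrease ≥10 <50 and decrease ≥15", and its high criteria, with the age bound, read "≥129 and increase ≥20 >13 Higha ≥86 and increase ≥10 >120 and increase ≥15".

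On eligibility, protocol inclusion criterion 36 covers participants "to <12 years of age at the time of screening, or are 12 to 17 and weighing <40 kg". SAP section 5.3 sets a ceiling for the older group: "Participants who are 12 to 17 years (and weighing <40 kg) can be enrolled, up to approximately 20 participants". The minimum of 5 per age group in the same section applies only to the three groups under 12. SAP section 6.12 takes the safety population as the denominator for percentages.

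**The concern.** A flagging rule for a safety tabulation should assign every eligible participant to exactly one row. Here the second-oldest row stops at 12 and the oldest is printed as strictly above 13. A 13-year-old under 40 kg can enrol and be dosed, but has no limit to be compared with. A program written literally from the table would leave that participant unflagged on all six criteria while still counting them in the denominator, so the tabulated percentage could only be too low.

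A programmer who noticed the gap would have to choose a row, and the choice can change the result because the neighbouring rows carry different limits. The arm is open-label and safety is its secondary objective, so the assignment should be fixed in the plan and not settled once data are visible.

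**Working it through.** The plan states no figure to reproduce. The check is whether the printed rows cover the eligible ages.

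**1. Completed years, rows as printed.**

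| Row | Ages covered |
|---|---|
| Infant <2 | 0, 1 |
| Child 2-4 | 2, 3, 4 |
| Child 5-9 | 5 to 9 |
| Child 10-12 | 10, 11, 12 |
| Adolescent >13 | 14 to 17 |

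From 0 to 17, age 13 is the only age without a row, and no age falls in two rows.

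**2. Exact (decimal) age, rows as printed.** There are gaps between 4 and 5, between 9 and 10, and above 12 up to and including 13.0. A participant aged 13.1 would be covered. The rows 2-4, 5-9 and 10-12 meet only in completed years, so that is the natural reading, but the SAP does not state it for this table. Its other age groupings are half-open intervals, and the protocol's schedule of activities collects full date of birth, so exact age could be computed.

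**3. Last row changed to ≥13.** In completed years every age from 0 to 17 falls in exactly one row. In exact age the gaps 4-5, 9-10 and 12-13 remain, so the age convention needs stating even if the original already prints ≥13.

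**4. Does the choice of row matter?** Two illustrative 13-year-olds:

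| Measurement | Child 10-12 row | Adolescent row | As printed |
|---|---|---|---|
| Pulse rises by 20 to 130 | Not flagged (needs >140 and rise ≥25) | Flagged (needs >120 and rise ≥15) | No row |
| Systolic falls by 20 to 88 | Not flagged (needs ≤85 and fall ≥20) | Flagged (needs ≤90 and fall ≥20) | No row |

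**5. How many participants?** The documents give no age mix. With n participants aged 12-17 (ceiling about 20, no minimum) and an assumed share s aged 13, the number affected is n × s.

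- n or s near zero: none affected.
- n = 20, s = 10%: 20 × 0.10 = 2, which is 2/70 = 3% of about 50 + 20 = 70 participants.
- n = 20, s = one third: 20 × 1/3 = 6.7, or about 7, which is 6.7/70 = 10%.

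The shares are assumptions chosen to show a range, and n = 20 is the ceiling. To turn a share into an understated event rate, one would also have to assume that 13-year-olds have the same event rate as the others, which the documents do not say.

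**The case against.** **The sign may be a reading artefact.** The text of the table is scrambled: the bound >13 is detached from the word Adolescent and stands between two limits. The inequality signs are also uneven. The infant low diastolic limit reads <35, where the other four rows use ≤. A printed ≥13 therefore cannot be excluded, and with it there would be no gap in completed years. This stands as a reason to check the original before acting. It does not dispose of the point: ≥ survives several times in the same row, nothing else in the documents assigns age 13 to a row, and the age convention is unstated under either sign.

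**The consequence is easily overstated.** A reader might infer that 13-year-olds can never be counted as having any treatment-emergent vital-sign abnormality. The documents do not support that:

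- The table covers blood pressure and pulse only. SpO2 has its own treatment-emergent summary without age bands (SAP 6.16.2.5).
- Clinical events reported as adverse events appear in the treatment-emergent, serious and infusion-reaction summaries (SAP 6.12.3), which do not use this table.
- The shift tables in Table PYAB.6.9 name the central laboratory service as the source of limits, and the box and scatter plots are not age-banded.

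These displays remain, but none replaces the missing categorical criterion. The table footnote, which permits analyses on change from baseline alone, fills the gap only in part. It is optional, with circumstances undefined. Its systolic and diastolic change limits agree across the two oldest rows (20 and 10), but its pulse limits do not (25 against 15).

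**The gap need not fall where adolescents are most numerous.** A reader might reason that the 40 kg limit favours the youngest adolescents. If so, the most frequent age would be 12, which the Child 10-12 row covers in completed years.

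**Conclusion.** The point holds in a limited form and is minor. As the table reads, and in completed years, age 13 is the one eligible age without a categorical blood pressure or pulse criterion. It affects one descriptive tabulation in a single-arm cohort with no decision rule attached to it. The number of participants is unknown and runs from zero to a few; the documents do not support a specific share or a specific bias in the rate.

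The conclusion rests on two things: that >13 is the printed label, which is likely but unconfirmed, and that age is counted in completed years, which the row structure implies but the SAP does not say. It is probably a typographical slip. It is still worth correcting, because the table is the stated basis for flagging and a literal program would follow it.

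**What to change.** 1. Check the label of the last row of Table PYAB.6.10 against the original SAP.
2. If it reads >13, make the age bands contiguous so that age 13 falls in exactly one row. The row name Adolescent suggests ≥13; the sponsor should confirm this, since the documents do not say which row was meant.
3. Under either sign, add a clause that the rows use age in completed years at screening, the time point that SAP section 5.3 already uses for age groups.

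The cost is at most one character and one clause in the SAP. No blood pressure or pulse limit changes and no further data are collected.
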